1. ABBREVIATIONS

ACC	American College of Cardiology
ACS	Acute Coronary Syndrome
AE	Adverse event
AR	Adverse reaction
ARC	Academic Research Consortium
BARC	Bleeding Academic Research Consortium
BMS	Bare Metal Stent
BP	Blood Pressure
CABG	Coronary Artery Bypass Graft
CCU	Coronary Care Unit
CK-MB	Creatine Kinase-MB
CRO	Contract Research Organisation
CT	Computerised Tomography
e-CRF	electronic Case Report Form
DAPT	Dual antiplatelet therapy
DES	Drug Eluting Stent
EAC	Event adjudication Committee
EC	Ethics Committee
ECG	Electrocardiogram
ESC	European Society of Cardiology
FDA	Food and Drug Administration
GCP	Good Clinical Practice
eGFR	estimated Glomerular Filtration Rate
ICH	International Conference of Harmonisation
MI	Myocardial infarction
NSTE	Non ST Elevation
PCI	Percutaneous Coronary Intervention
SAE	Serious Adverse Event
ST	Stent Thrombosis
STE	ST Elevation
Tn	Troponin
ULN	Upper Limit of Normal Range

2. BACKGROUND AND RATIONALE

Every year more than 1 million PCIs are performed in United States and similar numbers in Europe^{1,2}. In more than 85% of cases a coronary stent is implanted³, with the ensuing need for prolonged antiplatelet therapy in order to prevent stent thrombosis (ST). The international Practice Guidelines recommend dual antiplatelet therapy (DAPT) with aspirin and a P2Y₁₂ receptor antagonist for at least one month after bare metal stent (BMS) implantation and for 6 months after drug eluting stent (DES)^{4,5}. In patients with acute coronary syndrome (ACS), DAPT should be prolonged up to 12 months.

Premature discontinuation of antiplatelet therapy is associated with a significant increase in the risk of ST⁶⁻⁹, an infrequent but lifethreatening event which occurs most of the times as acute myocardial infarction (MI), with a mortality rate of 10-40%. The single most important predictor of ST is the cessation of antiplatelet therapy¹⁰⁻¹². Previous studies demonstrated that premature discontinuation of antiplatelet therapy (permanent or transitory) after stent implantation occurs in 10-50% of patients^{7,13}, most frequently due to surgical interventions¹³.

It has been estimated that 4-8% of patients submitted to stent implantation undergo surgery within the first year³. The perioperative management of antiplatelet therapy represents a relevant issue, not only as it is epidemiologically relevant, but also because it may have significant clinical consequences¹⁷. A patient who experiences a perioperative MI has an inhospital mortality of 15-25%¹⁸⁻²⁰.

Perioperative management of antiplatelet therapies raises important challenges and safety concerns. On one hand, withholding therapy to reduce the risk of bleeding complications is associated with a heightened risk of ischemic events, including life-threatening stent thrombosis (ST), myocardial infarction (MI) and stroke [8-10]. Surgery leads to inflammatory, hypercoagulable and hypoxic states which are associated with plaque instability and perioperative

arterial thrombosis^{3,14}. Thus, the perioperative risk of ST and other cardiac ischemic events is high, particularly if antiplatelet therapy is discontinued^{15,16}. On the other hand, maintaining antithrombotic therapy may increase the risk of bleeding and the need for transfusions, which are both known determinants of poor prognosis [3-10].

Defining the trade-off between ischemia and bleeding requires not only an understanding of the thrombotic risk of the individual patient, typically defined by the cardiologist, but also a clear understanding of the hemorrhagic risk specific to each surgical procedure, which requires the expertise of the surgeon. Although guidelines provide recommendations with respect to the perioperative management of antiplatelet and anticoagulant drugs, these have been developed primarily by cardiologists who may be less informed of the inherent bleeding risk of specific surgical procedures [11, 12]. Therefore, the surgical point of view is essential when it comes to issuing recommendations on how to manage antithrombotic therapies in the perioperative period. However, characterization of the perioperative bleeding risk of each surgical procedure is an area not addressed by current guidelines [11, 12].

On this background, the Italian Society of Interventional Cardiology (GISE) has previously promoted the creation of a task force integrating the expert opinions from a multidisciplinary collaboration between cardiologists, anesthesiologists, hematologists and surgeons, providing recommendations on the antithrombotic treatment regimen to be used in patients treated with coronary stents undergoing surgical and endoscopic procedures [13]. In particular, this led to the creation of a consensus document, called Surgery after Stenting (SAS), which provided practical recommendations for standardizing the approach to antithrombotic therapy management with respect to various types of surgery based on the predicted individual risk of thrombotic complications against the anticipated risk of surgical bleeding complications. A national registry surveyed the applicability of the recommendations in real-world clinical practice and supported

the relative merit of a risk stratification approach for both ischemia and bleeding in patients with coronary stents undergoing cardiac and NCS [21]. However, the landscape of devices, antithrombotic drugs, and surgical techniques has changed over the past years. In particular, the advent of the newer generation of DES has been associated with a remarkable risk reduction of ST, potentially allowing for a safe shorter DAPT duration, particularly in low ischemic risk patients [12, 22, 23]. On the other hand, data have shown potential for a protective effect of prolonged DAPT duration in high-risk settings [12, 22, 23]. The POISE-2 trial, investigating the effects of perioperative aspirin use, showed that this had no significant effect on the combined risk of death or nonfatal MI in patients undergoing non-cardiac surgery [24]. Nevertheless, it is important to note that only one patient out of four in this study had a history of coronary artery disease and only 4% of randomized patients had previously received coronary stents. Moreover, patients with implantation of DES within 1 year and BMS <6 weeks were excluded. Due to this limitation, the results of the POISE-2 trial should not be applied to patients with previous coronary stent implantation. Thus, while being an important study, it should not be considered when managing perioperative antiplatelet therapy in patients with coronary stents undergoing surgery.

The SAS 2 Consensus Document derives from a multidisciplinary collaboration and provides practical recommendations on the perioperative management of antithrombotic therapy in patients treated with coronary stents. These recommendations are summarized in the present document and can be accessed through a workable web application, which can be downloaded at <https://itunes.apple.com/us/app/stent-surgery/id551350096?mt=8>. The Writing Committee was composed of cardiologists, surgeons, anesthesiologists, and hematologists. Overall, the recommendations summarized in this document were finally endorsed by 23 scientific societies, including interventional cardiology (n=1), anesthesiology (n=1), hematology (n=1), and a number of surgical specialties (n=20).

Cardiologists defined the thrombotic risk based on a series of clinical features and procedural characteristics. In particular, the definition of thrombotic risk (low, intermediate or high) was derived after careful revision of the literature which led to the formulation of a tables which summarized the information obtained. All Cardiology members of the Writing Committee provided their feedback until a consensus was reached. Surgeons classified all interventions according to the inherent hemorrhagic risk (low, intermediate, or high) of each specific surgery. In particular, bleeding risk was not solely based on the amount of blood loss, but mostly according to the anticipated difficulty in achieving adequate local hemostasis. The bleeding risk was defined in a total of about 250 surgical procedures. Finally, the most appropriate antithrombotic treatment regimen in the perioperative phase was defined for each procedure taking into consideration both the thrombotic and bleeding risk profiles. Ultimately, a consensus agreement was reached which involved not only cardiologists and surgeons, but also anesthesiologists and hematologists. Importantly, the recommended antithrombotic treatment regimen was not standard to a given thrombotic/bleeding risk profile, but was specific to each individual surgical specialty.

In general, if surgery cannot be delayed, it should be performed after the first month and ideally after at least 3 months from PCI [25, 32, 46, 49]. The vast majority of procedures may be performed while on aspirin, with the possible exception of surgeries at extremely high risk of bleeding (e.g., neurosurgery). When a wash-out of P2Y12 inhibiting therapy is required, this should be performed judiciously according to the timing of surgery: 5 days for clopidogrel and ticagrelor and 7 days for prasugrel. Recent data from a large observational study in CABG patients demonstrated that discontinuation 3 days before surgery, as opposed to 5 days, did not increase the incidence of major bleeding complications with ticagrelor (OR 0.93 (95% CI 0.53-1.64), p=0.80), but increased the risk with clopidogrel (OR 1.71 (95% CI 1.04 – 2.79), p=0.033 [71]. On the basis of these findings, in selected cases, surgery might be performed after 3 days of

ticagrelor discontinuation.

In selected cases, according to the SAS 2 recommendations, a bridging of antiplatelet therapy should be considered. A bridge therapy indicates a strategy of temporary transition with an intravenous antiplatelet agent in patients on oral antiplatelet therapy typically consisting of aspirin and a P2Y12 inhibitor. This strategy is usually reserved for patients deemed at high thrombotic risk (who thus cannot safely interrupt oral antiplatelet therapy) undergoing non-deferrable surgery at high risk of bleeding, which requires a predictable interruption of platelet inhibition at the time of the intervention [3-6].

The only intravenous antiplatelet agents available for clinical use, and thus of potential utility for antiplatelet bridging, include cangrelor and glycoprotein IIb/IIIa inhibitors (GPI). Cangrelor is an intravenous analog of adenosine triphosphate with a potent, selective and specific affinity for P2Y12 receptors [63]. Given that cangrelor is not renally cleared, there is no need for dose adjustment in patients with impaired renal function. Reversible binding to P2Y12 receptors of this agent along with its very short half-life (3-6 minutes) allows for resumption of platelet function within 60 minutes of infusion cessation [64]. Cangrelor was recently approved for the reduction of thrombotic cardiovascular events in patients with CAD undergoing PCI who have not received an oral P2Y12 inhibitor prior to the PCI [65]. Cangrelor has also been specifically tested against placebo as a bridging agent among thienopyridine-treated patients undergoing coronary artery bypass grafting surgery (CABG) in the Bridging Antiplatelet Therapy With Cangrelor in Patients Undergoing Cardiac Surgery (BRIDGE) trial [66]. In conclusion, in line with the BRIDGE trial approach, if intended as a bridging agent, cangrelor can be commenced any time between the next expected dose of the P2Y12 inhibitor and within 72 hours from P2Y12 inhibitor discontinuation, and stopped up to 1 hour before the start of surgery.

Alternatively, small molecule GPI's (eptifibatide or tirofiban) may be considered for bridging therapy [67]. Compared with cangrelor however, these agents have a slower offset of

action and they do not target the P2Y12 receptor. In addition, since they are renally cleared, dose adjustments are required among patients with impaired renal function. There are no randomized trials on bridging with small molecule GPIs and data derive from observational studies. Infusion should be commenced three days prior to surgical intervention, whereas clopidogrel and ticagrelor should be discontinued five days prior to surgery and seven days with prasugrel. GPI infusion should be interrupted at least four hours prior to surgery (eight hours in patients with creatinine clearance <30 ml/min).

P2Y12 inhibitors resumed within 24-48 hours after the intervention after confirmation of successful hemostasis, and with a loading dose. In patients with an increased bleeding risk in the post-operative period, clopidogrel should be preferred over prasugrel or ticagrelor. If gastrointestinal function has not yet recovered (e.g., abdominal surgery), intravenous infusion of antiplatelet agents (cangrelor or GPI) should be restarted after the surgical procedure, after careful evaluation of the bleeding risk. After complete intestinal recanalization, therapy with P2Y12 inhibitors should be resumed with a loading dose, after which the infusion of intravenous antiplatelet agents can be stopped. Because thrombotic complications occur most frequently soon after surgery, close post-operative clinical and electrocardiographic monitoring is strongly encouraged.

Notably, the impact of the application of the SAS 2 document on perioperative antiplatelet therapy in clinical practice has not been evaluated.

3. OBJECTIVES

3.1 Primary Objective

- To assess outcomes associated with the application of the Consensus Document “Stent and Surgery-2” on perioperative antiplatelet therapy in patients with coronary stenting undergoing surgery.

3.2 Secondary Objectives

- To assess ischemic and hemorrhagic events in relation to the application of the Consensus Document. Length of any antiplatelet discontinuation and delay in performing surgical procedures will also be evaluated.

4. STUDY DESIGN

4.1 Summary of Study Design

The SAS registry will include any patient with previous coronary stenting undergoing any type of surgery or operative endoscopic/endovascular procedure at the participating Centers. Centers will be divided into two groups: Centers that routinely follow the recommendations of the SAS 2 Document and Centers that do not. The relevant clinical, procedural and outcome data (within index admission and at 30 days) will be entered in a specifically designed electronic case record form (eCRF).

4.2 Primary endpoint

- Rate of discontinuation of P2Y12 inhibitors and/or aspirin (without bridging) in the first 3 months after PCI with low risk characteristics and 6 months after PCI with high risk characteristics or any antiplatelet therapy discontinuation without bridging therapy

4.3 Secondary endpoints

Patients undergoing non cardiac surgery:

- The composite of death, myocardial infarction, probable/definite stent thrombosis according the Academic Research Consortium definition⁴⁴ and bleeding events of Bleeding Academic Research Consortium (BARC) grade ≥ 3 at 30 days
- The composite of death, myocardial infarction and probable/definite stent at 30 days
- The incidence of bleeding events of Bleeding Academic Research Consortium (BARC) grade ≥ 3 at 30 days
- The type and the length of discontinuation of any antiplatelet therapy in patients undergoing non cardiac surgery according to time from PCI to surgery
- Rate of non cardiac surgical procedures within 12 months from PCI divided into quartiles (0-3, 3-6, 6-9, 9-12 months)
- Delay in performing non cardiac surgical procedure

Patients undergoing cardiac surgery:

- The composite of death, myocardial infarction, probable/definite stent thrombosis according the Academic Research Consortium definition⁴⁴ and bleeding events of Bleeding Academic Research Consortium (BARC) grade ≥ 4 at 30 days
- The composite of death, myocardial infarction and probable/definite stent at 30 days
- The incidence of bleeding events of Bleeding Academic Research Consortium (BARC) grade ≥ 4 at 30 days
- The type and the length of discontinuation of any antiplatelet therapy in patients undergoing cardiac surgery according to time from PCI to surgery
- Rate of cardiac surgical procedures within 12 months from PCI divided into quartiles (0-3, 3-6, 6-9, 9-12 months)
- Delay in performing cardiac surgical procedure

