6.4 Bleeding Classification

All bleeding events will be considered in patients undergoing cardiac and non cardiac surgery.

Bleeding events will be classified according to BARC classification.

Bleeding Academic Research Consortium Definition for Bleeding (Ref 43)

- Type 0: no bleeding
- Type 1: bleeding that is not actionable and does not cause the patient to seek unscheduled performance of studies, hospitalization, or treatment by a healthcare professional; may include episodes leading to self-discontinuation of medical therapy by the patient without consulting a healthcare professional

- Type 2: any overt, actionable sign of hemorrhage (eg, more bleeding than would be expected for a clinical circumstance, including bleeding found by imaging alone) that does not fit the criteria for type 3, 4, or 5 but does meet at least one of the following criteria: (1) requiring nonsurgical, medical intervention by a healthcare professional, (2) leading to hospitalization or increased level of care, or (3) prompting evaluation

- Type 3

Type 3a: overt bleeding plus hemoglobin drop of 3 to <5 g/dL* (provided hemoglobin drop is related to bleed); any transfusion with overt bleeding

Type 3b: overt bleeding plus hemoglobin drop ≥ 5 g/dL* (provided haemoglobin drop is related to bleed); cardiac tamponade; bleeding requiring surgical intervention for control (excluding dental/nasal/skin/hemorrhoid); bleeding requiring intravenous vasoactive agents

Type 3c: intracranial hemorrhage (does not include microbleeds or hemorrhagic transformation, does include intraspinal); subcategories confirmed by autopsy or imaging or lumbar puncture; intraocular bleed compromising vision

- Type 4: CABG-related bleeding, including perioperative intracranial bleeding within 48 h, reoperation after closure of sternotomy for the purpose of controlling bleeding, transfusion of >5 U whole blood or packed red blood cells within a 48-h period, chest tube output >2L within a 24-h period
- Type 5: fatal bleeding

Type 5a: Probable fatal bleeding; no autopsy or imaging confirmation but clinically suspicious

Type 5b: Definite fatal bleeding; overt bleeding or autopsy or imaging confirmation

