7.2 Description of Statistical Methods

Continuous numeric variables will report as means with SD and compared using the Student’s t- or Wilcoxon rank-sum test. Categorical variables will be presented as counts and percentages and will be compared using the chi-square or Fisher’s exact test. To examine the effect of significant factors on two different groups (Group 1 vs Group 2) the hazard ratio of the interaction term will be calculated. To identify the independent predictors for in hospital NACE, 30day MACE and 30-day BARC bleedings, first univariate and then multivariate logistic regression models will apply. The BARC bleedings will be considered according to type of surgery. Specifically, BARC bleedings grade ≥ 3 will be considered in patients undergoing cardiac surgery, and BARC bleedings grade ≥ 4 will be taken into account for non-cardiac surgery. Covariates for multivariable models will be selected on the basis of a backward stepwise algorithm in a Cox proportional hazards model. Additionally, to minimise group differences on confounding covariates between patients who will be managed with consensus document (group 1) and those who will be received local practice (group 2), a 1:2 propensity score matching would be used. Propensity scores will be calculated with logistic regression, with multiple imputation and backwards elimination with a significance level to stay of 0.05. To ensure that the comparison between two groups (group 1 vs group 2) would not be bias, the proportion of patients who will not received consensus document within center that traditionally used it, will be excluded. The results will be presented as ORs with 95% confidence intervals (CI) and p values. For all

analyses, a two-sided $P <0.05$ will be required for statistical significance. All data will be analyzed using the Statistical Package of Social Sciences version 20 (IBM SPSS, Chicago, IL).

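### The ≥ 4 bleeding cut for cardiac surgery conflicts with section 7.2 and, read with section 6.4, leaves some non-fatal major bleeds after CABG uncounted

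*Combined protocol and SAP*

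**What the plan says.** Section 4.3 sets separate secondary endpoints for the two surgery groups. For cardiac surgery the stand-alone bleeding endpoint is "The incidence of bleeding events of Bleeding Academic Research Consortium (BARC) grade ≥ 4 at 30 days". The net composite joins death, myocardial infarction and stent thrombosis with "bleeding events of Bleeding Academic Research Consortium (BARC) grade ≥ 4 at 30 days". For non-cardiac surgery the corresponding cut in 4.3 is ≥ 3.

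Section 7.2 assigns the cuts the other way round: "BARC bleedings grade ≥ 3 will be considered in patients undergoing cardiac surgery". Its cut for the non-cardiac group is ≥ 4.

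Section 6.4 gives the BARC definitions. Two entries matter most here:
- "Type 4: CABG-related bleeding, including perioperative intracranial bleeding within 48 h". The other listed criteria are reopening of the sternotomy to control bleeding, "transfusion of >5 U whole blood or packed red blood cells within a 48-h period", and chest drainage above 2 L in 24 hours.
- "Type 3c: intracranial hemorrhage (does not include microbleeds or hemorrhagic transformation, does include intraspinal", with no time limit.

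Type 3b, also without a time limit, covers overt bleeding with a haemoglobin fall of at least 5 g/dL, tamponade, and bleeding that needs surgery or intravenous vasoactive drugs. Type 5 is fatal bleeding.

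**The concern.** There are two linked problems. First, 4.3 and 7.2 give opposite thresholds, so the plan does not settle which bleeds count in either surgery group. Second, the version in 4.3 works only if type 4 is the next step in severity above type 3. In 6.4 it is not: type 4 is defined by its setting (CABG), and types 3b and 3c contain severe bleeds. A cut at ≥ 4 therefore selects partly on setting and timing.

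At stake is what the 30-day bleeding endpoint and the bleeding part of the net composite measure after cardiac surgery. A secondary objective (3.2) is to assess ischaemic and haemorrhagic events in relation to use of the consensus document. Death, infarction and stent thrombosis count for the full 30 days. The intracranial criterion of type 4 closes at 48 hours, which is about when the Background describes P2Y12 inhibitors being resumed (24 to 48 hours after the intervention). Some serious non-fatal bleeding in the remaining four weeks would not register.

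**Working it through.** The plan gives no figure to reproduce, because this is a question of definitions. The inputs are the two cuts (4.3 and 7.2) and the type criteria (6.4).

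**Step 1. The thresholds side by side.**

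| Surgery group | Section 4.3 | Section 7.2 |
|---|---|---|
| Cardiac | ≥ 4 | ≥ 3 |
| Non-cardiac | ≥ 3 | ≥ 4 |

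The two columns cannot both hold.

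**Step 2. Example bleeds after CABG, classified from 6.4.** Each bleed takes the highest type whose criteria it meets.

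| Bleed | Highest type | Counted at ≥ 4 | Counted at ≥ 3 |
|---|---|---|---|
| Non-fatal intracranial, hour 24 | 4 | yes | yes |
| Non-fatal intracranial, day 5 | 3c | **no** | yes |
| Fatal intracranial, day 5 | 5 | yes | yes |
| Non-fatal gastrointestinal, Hb fall 6 g/dL, 4 U in 48 h | 3b | **no** | yes |
| Same bleed with 6 U in 48 h, if judged CABG-related | 4 | yes | yes |
| Non-fatal retroperitoneal, needing surgery, no transfusion | 3b | **no** | yes |
| Non-fatal tamponade, sternotomy not reopened | 3b | **no** | yes |
| Sternotomy reopened for bleeding | 4 | yes | yes |

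The first two rows differ only in timing. The two gastrointestinal rows differ only by 2 U of blood, because the transfusion criterion requires more than 5 U.

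**Step 3. The same bleed in the other surgery group.** Under 4.3 non-cardiac surgery uses ≥ 3. The gastrointestinal bleed with 4 U, not counted after CABG, is therefore counted after a non-cardiac operation.

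**Step 4. Where type 4 may not apply.** Type 4 is worded as CABG-related. Read literally, for cardiac surgery other than CABG a cut at ≥ 4 leaves only type 5, fatal bleeding. The same follows for all non-cardiac surgery under the ≥ 4 cut in 7.2.

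**Step 5. Size.** Let x be the rate of uncounted type 3b/3c events and r the rate of type 4 or 5 events. If no patient has both, the proportion missed is x / (x + r). The documents give neither rate. Purely as an assumption, x = 0.5% with r = 10% gives 0.5 / 10.5 = 5%, and x = 2% with r = 5% gives 2 / 7 = 29%. That spread reflects the assumed values and is not an estimate for this registry.

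**The case against.** The strongest objection is that 7.2 already uses ≥ 3 for cardiac surgery, and at ≥ 3 every bleed in the table counts. If the sponsor reconciles to that, the gap closes. This stands as far as it goes, but the endpoint section says otherwise. The ≥ 4 cut that 7.2 gives for non-cardiac surgery would, read literally, leave only fatal bleeding there, so a transposition in 7.2 is plausible. Correcting 7.2 to match 4.3 would fix the omission in place. The documents do not show which section was intended.

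The gap also has limits. Fatal bleeds are type 5 and count. The transfusion criterion of type 4 names no site, so a heavily transfused bleed away from the chest can qualify if judged CABG-related. The type 4 list is introduced as inclusive, so adjudicators may have latitude. Patients can still enter the net composite through death, infarction or stent thrombosis. Major bleeding, transfusion and reoperation are captured in the eCRF (4.5.3), so the underlying data are not lost. These are secondary endpoints in a subgroup of unstated size; the primary endpoint is antiplatelet discontinuation.

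A reader might infer three stronger points, which the documents do not support:
- **Every major bleed away from the chest is missed.** The limits above show otherwise.
- **The rule breaks a commitment in 6.4.** The sentence "All bleeding events will be considered in patients undergoing cardiac and non cardiac surgery" opens a classification section. It does not say that every type enters every endpoint, and even the ≥ 3 cut would fail that reading.
- **The comparison is biased towards more intensive therapy.** Groups are defined by use of the consensus document. Nothing shows that its use means more intensive therapy in cardiac surgery, or how the missed bleeds would divide between groups.

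**Conclusion.** The point holds in a limited form. Sections 4.3 and 7.2 contradict each other on the bleeding threshold in both surgery groups. If 4.3 governs, two kinds of non-fatal bleed after CABG drop out of the 30-day bleeding endpoint and of the bleeding component of the net composite: intracranial haemorrhage after 48 hours, and type 3b bleeding unrelated to the operative field that meets no type 4 criterion. This rests on reading the listed type 4 criteria as the working definition; wider adjudicator discretion would narrow the gap but leave like bleeds open to different scoring. No size or direction can be given, because the documents contain no bleeding rates by type. The defect should be corrected, but it does not touch the primary endpoint.

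**What to change.** Replace the numeric cuts with an explicit list of qualifying BARC types for each surgery group, worded identically in 4.3 and 7.2.

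- **Cardiac surgery:** type 4 or 5, or type 3c at any time, or type 3b not arising from the operative field. Report the ≥ 4 version as a sensitivity analysis. Listing types 3, 4 and 5, as the ≥ 3 cut in 7.2 implies, would also close the gap, but it would admit type 3a and operative-field type 3b bleeding as well.
- **Cardiac surgery other than CABG:** state how operative-field bleeding is classified, since type 4 is worded for CABG. Otherwise a reoperation for bleeding could fall to operative-field type 3b and be excluded under the first list.
- **Non-cardiac surgery:** name the types in the same way, so that 4.3 and 7.2 agree.

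Make the change before any comparison by group is seen, so that the definition is not chosen after the results.

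The cost is a definition edit in two sections, a slightly higher event rate, and one extra adjudicated item (bleeding site). Section 11.2 already has the Event-adjudication Committee review source documents, from which the site could be read. It does not say that the committee assigns the BARC type, so that should be stated as well.
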